11.3 Discontinuation Criteria

A subject may be discontinued from the study or study drug for any of the following reasons:

- Withdrawal of consent by the subject and/or subject's legal guardian;
- Investigator or sponsor decision that withdrawal is in the subject's best interest;
- Occurrence of an AE that, in the opinion of the investigator, warrants discontinuation of the subject from the study drug;
- Lost to follow-up (every attempt should be made to contact the subject).

A subject will be discontinued from the study for any of the following reasons:

- Absence of culture-confirmed *Candida* spp. infection from the sample collected at Screening as reviewed at Baseline (Day 1)
- Failure to continue to meet all eligibility criteria at Baseline (Day 1)
- Occurrence of pregnancy

A subject will be discontinued from the study and will enter the Nested Sub-Study (see [Section 21.3](#) [Appendix C]) for the following reason:

- Positive fungal cultures at Screening with persistence of signs and symptoms of infection (total composite score ≥ 3 on the VSS Scale) at Baseline (Day 1), following treatment with open-label fluconazole

Subjects with Recurrences (Mycologically Proven, Presumed or Suspected) of VVC will not be discontinued from the study but will receive rescue antifungal medication, continue their study drug administration (if during the Study Treatment Phase) and complete all their scheduled visits until reaching EOFU.

The reason for a subject's discontinuation of treatment or withdrawal from the study will be clearly documented in the source documents and on the electronic case report form (eCRF). At the time of discontinuation, all Week 24 (TOC) procedures should be performed for subjects who discontinue from the study on or before the Week 24 (TOC) visit and all Week 36 (EOFU) procedures should be performed for subjects who discontinue from the study after the TOC visit but on or before the EOFU visit.

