7.2.3 Rationale for Study Endpoints and Efficacy Outcomes

In this study, recurrent VVC will be broken into three categories:

- **Mycologically Proven Recurrence:** An episode of VVC with a total composite score ≥ 3 on the VSS Scale and a culture positive for *Candida* spp. that required antifungal treatment.
- **Presumed Recurrence:** An episode of VVC with a total composite score ≥ 3 on the VSS Scale that required antifungal treatment and for which there is a positive KOH microscopy but no positive fungal culture.
- **Suspected Recurrence:** An episode of VVC that required treatment with an antifungal agent (including self-administration with over-the-counter antifungals) regardless of VSS composite score but for which there is no mycological evidence of disease, such as a positive potassium hydroxide (KOH) microscopy or fungal culture.

The primary endpoint of the study will be the percentage of subjects with documented Clinical Success (defined as subjects having a TOC evaluation and no Mycologically Proven, Presumed or Suspected Recurrence of VVC) up to TOC (Week 24). This criterion is meant to reflect real world practice, where patients may self-treat, and apply scientific rigor in assigning subjects with signs and symptoms of disease, regardless of culture result or missing data, as failures.

The key secondary endpoint will be the percentage of subjects with no Mycologically Proven Recurrence at TOC (Week 24). The key secondary endpoint is based on recurrences that are symptomatic and required antifungal therapy. This criterion is aimed at reflecting the highest level of certainty in the diagnosis of a recurrence in a symptomatic subject seeking medical treatment. This endpoint is anticipated to objectively demonstrate the antifungal activity of ibrexafungerp.

These endpoints are considered appropriate to identify the key clinical benefit intended with this preventive regimen.

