10.1.1.3.3 Recurrence During the Prevention of Recurrence Phase

The occurrence of a recurrence is the key efficacy parameter in this study. Randomized subjects will be assessed for potential recurrence at all visits during the Prevention of Recurrence Phase following Day 1 (Baseline) (i.e., from Day 2 through Week 36 [EOFU]), including phone contacts, scheduled visits and unscheduled visits, as well as in between visits. If during a phone contact or at any other time there is suspicion of a potential recurrence (any kind of recurrence, i.e., Mycologically Proven, Presumed or Suspected), subjects will be instructed to visit the study center for a proper evaluation of their recurrence before initiating any VVC treatment.

Potential recurrences will be assessed based on clinical and mycological outcomes and need for other antifungal treatment. If a subject has symptoms suggestive of *Candida* infection (itching, burning, irritation) that in the opinion of the investigator may require antifungal therapy, the following procedures must be completed:

- Rate and document symptoms in the electronic case report form (eCRF),
- Perform vaginal examination to rate signs and document in the eCRF,
- Measure vaginal pH at the site and document results in the eCRF,
- Collect vaginal sample for KOH testing and investigation of potential bacterial vaginosis and *Trichomonas vaginalis* infection at the site or by the local laboratory, and
- Collect vaginal samples for fungal culture by the central laboratory.

All of the procedures above should be completed prior to administration of rescue antifungal medication. Subjects participating in the study should be strongly discouraged from self-administering any treatment for a potential recurrence. Ideally, if the severity of the symptoms allows based on the investigator's judgment, the initiation of antifungal therapy should be delayed until results from the vaginal culture are available to confirm that the episode is due to *Candida* spp. and not to other cause of vaginitis.

See [Section 14.18](#) for a detailed description of procedures to be completed for potential recurrences.

In this study, Recurrences of VVC will be broken into three categories:

- **Mycologically Proven Recurrence:** An episode of VVC with a total composite score ≥ 3 on the VSS Scale and a culture positive for *Candida* spp. that required antifungal treatment.

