- **Presumed Recurrence:** An episode of VVC with a total composite score ≥ 3 on the VSS Scale that required antifungal treatment and for which there is a positive KOH microscopy but no positive fungal culture.
- **Suspected Recurrence:** An episode of VVC that required treatment with an antifungal agent (including self-administration with over-the-counter antifungals) regardless of VSS composite score but for which there is no mycological evidence of disease, such as a positive KOH microscopy or fungal culture.

Subjects with a **Mycologically Proven Recurrence** should receive antifungal therapy.

If a subject experiences one or more recurrences during the Study Treatment Period Phase (i.e., either a Mycologically Proven Recurrence, a Presumed Recurrence or a Suspected Recurrence), she will continue her scheduled study drug administration and will complete all scheduled visits until reaching EOFU.

All antifungal therapy administered during the study should be documented in the electronic data capture (EDC) system, with the reason for use clearly indicated (i.e., Mycologically Proven Recurrence, Presumed Recurrence, Suspected Recurrence).

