## **5. Subject Disposition**

### **5.1. Disposition**

A flowchart diagram includes the number of subjects who screened, subjects who screen failed before acute phase, subjects who entered acute phase, subjects who discontinued after acute phase,

subjects who entered the nested sub-study, subjects who entered the prevention of recurrence phase, will be presented.

For subjects who entered the nested sub-study, the following categories should be presented: subjects in each analysis set (ITT, mITT, SS), subjects who completed TOC visit, subjects who completed the study, subjects who discontinued from the study, and the reasons for study discontinuation.

For subjects who entered the prevention of recurrence phase, the following categories should be presented: subjects in each analysis set (ITT, mITT, PP, SS), subjects who completed TOC visit, subjects who completed the study, subjects who discontinued from the study, and the reasons for study discontinuation.

A disposition table of subjects includes the number and percentage of subjects for the following categories: subjects in each analysis set (ITT, mITT, PP, SS), subjects who completed TOC visit, subjects who completed the study, subjects who discontinued from the study, and the reasons for study discontinuation will be presented by the ITT and mITT sets. All percentages will be based on the number of subjects in each corresponding set.

The reason for study discontinuation may include any of the following: Absence of culture-confirmed *Candida* spp. infection from the sample reviewed at Baseline, Adverse Event, Lost to Follow-up, Physician Decision, Pregnancy, Study Terminated by Sponsor, Withdrawal by Parent or Guardian, Withdrawal by Subject, Other, Death, Trial Screen Failure.

Subject disposition data will be presented in a listing.

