### 8.1. Primary Endpoint

The primary efficacy endpoint is defined as the proportion of ITT subjects who have documented Clinical Success (defined as subjects having a TOC evaluation and no Mycologically Proven, Presumed or Suspected Recurrences of VVC) up to Week 24 (TOC).

Clinical success will be assessed according to the following definitions:

- Clinical success: Subjects having a TOC evaluation and no Mycologically Proven, Presumed or Suspected Recurrences of VVC prior to or at the TOC visit.
- Clinical failure: Mycologically Proven, Presumed or Suspected Recurrences of VVC prior to or at the TOC visit. For the subject who early terminated before TOC visit, the subject is considered a clinical failure.

Recurrence of VVC: In this study, Recurrence of VVC will be broken into three categories:

- Mycologically Proven Recurrence: An episode of VVC with a total composite score  $\geq 3$  on the VSS Scale and a culture positive for *Candida* spp. that required antifungal treatment.
- Presumed Recurrence: An episode of VVC with a total composite score  $\geq 3$  on the VSS Scale that required antifungal treatment and for which there is a positive KOH microscopy but no positive fungal culture.
- Suspected Recurrence: An episode of VVC that required treatment with an antifungal agent (including self-administration with over-the-counter antifungals) regardless of VSS composite score but for which there is no mycological evidence of disease, such as a positive KOH microscopy or fungal culture. It also includes an episode of VVC that requires antifungal treatment and have a total VSS composite score lower than 3 regardless of mycological results.

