#### 8.1.1. Primary Analysis

The primary efficacy analysis will be performed on the ITT set at the TOC visit and will compare the proportion of subjects, in the treatment and placebo groups, who have documented Clinical Success up to Week 24 (TOC).

The number and percentage of subjects with documented clinical success up to the TOC visit will be presented by treatment group. Meanwhile, the number and percentage of subjects with clinical

failure will be presented by the recurrence categories. A Cochran Mantel Haenszel (CMH) test adjusted for Country and uncontrolled diabetes mellitus (Yes or No) at baseline will be performed to assess the statistical significance of a difference between treatment groups in the primary efficacy analysis. Mathematically stated:

$H_0$ : Clinical Success Rate up to Week 24 (TOC) Oral ibrexafungerp 300-mg dose = Clinical Success Rate up to Week 24 (TOC) Placebo

$H_1$ : Clinical Success Rate up to Week 24 (TOC) Oral ibrexafungerp 300-mg dose  $\neq$  Clinical Success Rate up to Week 24 (TOC) Placebo

The p-value, relative risk and 95% confidence interval (CI) will be presented in the ibrexafungerp 300-mg treatment arm compared to the placebo arm. Subjects who have one or more of the required assessments of potential recurrence not completed prior to or at Week 24 (TOC) visit or subjects who withdraw from the study early will be imputed using the imputation rules described in [Section 4.4.1](#).

A sensitivity analysis using the ITT set will be performed where subjects with the imputed clinical outcome will be removed from the analysis.

Subgroup analyses will be performed in the ITT set depending on BMI category ( $\leq 35$  kg/m^2 or  $>35$  kg/m^2), geographic region (USA and EX-USA), Race (White, Black or African American, Asian, American Indian or Alaska Native, Native Hawaiian or Other Pacific Islander, and Other), Uncontrolled diabetes mellitus (Yes or No), Ethnicity (Hispanic or Latino, Not Hispanic or Latino), Number of recurrent VVC episodes in the prior year ( $<4$  times,  $\geq 4$  times) and Candida species at screening (by Genus species), severity of VVC at screening (2 categorizations of the composite score of the vulvovaginal signs and symptoms at screening will be used to evaluate the severity of VVC at screening:  $<7$ ,  $\geq 7$  and '4 - 7', '8 - 12', and ' $\geq 13$ ').

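### Protocol 11.3 lets a site take a woman off study for an AE that warrants only stopping study drug; if she leaves recurrence-free before TOC she is scored a failure, and no planned analysis supplies her Week 24 status

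*Protocol*

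**What the plan says.** **Leaving drug or study.** Protocol 11.3 opens its permissive list with "A subject may be discontinued from the study or study drug for any of the following reasons". The AE item reads "Occurrence of an AE that, in the opinion of the investigator, warrants discontinuation of the subject from the study drug". Nothing tells the site how to choose between the two kinds of discontinuation. SAP 5.1 includes AE among the possible reasons for study discontinuation: "infection from the sample reviewed at Baseline, Adverse Event, Lost to Follow-up, Physician Decision, Pregnancy".

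**Staying on visits.** Protocol 10.1.1.3.3 states generally that "Randomized subjects will be assessed for potential recurrence at all visits during the Prevention of Recurrence Phase", running to Week 36, and 14.18 repeats this. The explicit instruction to stay is narrower. A woman who has a recurrence is told that "she will continue her scheduled study drug administration and will complete all scheduled visits until reaching EOFU". The parallel statements in 10.1.1.3.1, 10.1.1.3.2, 11.3 and 14.18.3 are likewise triggered by recurrence or antifungal use. None is triggered by stopping study drug.

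**Scoring.** SAP 8.1: "For the subject who early terminated before TOC visit, the subject is considered a clinical failure". The only sensitivity analysis of the primary endpoint is in SAP 8.1.1: "A sensitivity analysis using the ITT set will be performed where subjects with the imputed clinical outcome will be removed from the analysis". Protocol 7.2.3 makes the failure rule deliberate, assigning symptomatic women, "regardless of culture result or missing data, as failures".

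**The concern.** Whether a woman recurs by Week 24 can be observed whether or not she is still taking tablets. If the site stops her drug and keeps her on visits, she can be an ITT success. If the site exits her for the same AE, she is a failure by rule. Two women with the same clinical course can therefore be scored oppositely, depending on how a site reads 11.3.

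At stake is avoidable missing data in the primary endpoint. The AEs reported with oral ibrexafungerp are mainly gastrointestinal (Protocol 7.1), so AE stops could be more frequent on active drug. Exits would then pull the estimated difference toward zero and cost power. Protocol 18.1 states no dropout allowance, and 11.4 says early discontinuers are not replaced.

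**Working it through.** **1. What each analysis does with a recurrence-free woman who exits before TOC**

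| Analysis | Handling |
|---|---|
| ITT primary (SAP 8.1, 8.1.1) | Failure |
| ITT sensitivity (SAP 8.1.1) | Removed |
| mITT (SAP 8.1.1) | Same imputation, failure |
| PP (SAP 4.3) | Excluded for lack of TOC data, or a failure if the AE is drug-related |
| Kaplan-Meier (SAP 8.2.1) | Recurrence-free time kept, censored at last assessment |
| Week 4, 8, 12 endpoints (SAP 4.4.1, 8.2.1) | Can count as recurrence-free if she left after that visit with assessments complete |
| Recurrence count (SAP 8.2.1) | Apparently included, since a completers-only version is listed as additional |

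The last three rows use what was observed. None gives her status at Week 24.

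**2. The plan's own figure.** Inputs from Protocol 18.0 and 18.1: 65% versus 43%, two-sided alpha 0.05, 1:1, about 240 subjects, Fisher's exact test. Exact enumeration at 120 per arm gives power 0.909, so the plan's figure is reproduced.

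**3. Illustration of size.** The stop rates s_a (ibrexafungerp) and s_p (placebo) are assumptions. The only related figure is zero AE discontinuations in the 600 mg arm of the Phase 2b DOVE study, over one dosing day (Protocol 7.1). The planned rates are taken as on-drug rates. Ibrexafungerp stoppers are assumed to revert to 43% if followed, and placebo stoppers to stay at 43%.

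- All exited: active = (1 − s_a) × 0.65; placebo = (1 − s_p) × 0.43
- All retained: active = (1 − s_a) × 0.65 + s_a × 0.43; placebo = 0.43

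At 5%/1% exited: 0.95 × 0.65 = 61.75% and 0.99 × 0.43 = 42.57%, difference 19.2 points. Retained: 61.75% + 0.05 × 43% = 63.90% versus 43%, difference 20.9 points.

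| s_a / s_p | Exited rates | Power, exited | Retained rates | Power, retained | Loss |
|---|---|---|---|---|---|
| 2% / 2% | 63.70% v 42.14% | 0.895 | 64.56% v 43% | 0.896 | about 0.002 |
| 5% / 5% | 61.75% v 40.85% | 0.872 | 63.90% v 43% | 0.875 | 0.003 |
| 2% / 1% | 63.70% v 42.57% | 0.882 | 64.56% v 43% | 0.896 | 0.014 |
| 5% / 1% | 61.75% v 42.57% | 0.807 | 63.90% v 43% | 0.875 | 0.068 |
| 8% / 2% | 59.80% v 42.14% | 0.733 | 63.24% v 43% | 0.851 | 0.118 |

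If only half the stoppers are exited, power is 0.843 at 5%/1% and 0.797 at 8%/2%.

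**4. Sensitivity to the reversion assumption.** If ibrexafungerp stoppers kept the full 65% when followed, retained power would be 0.909. The loss at 5%/1% becomes 0.909 − 0.807 = 0.102, and at 5%/5% it becomes 0.909 − 0.872 = 0.037.

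**5. Direction.** With 43% in both arms and 8%/2% exits, the chance of a significant result favouring ibrexafungerp falls from 1.8% to 0.7%.

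**The case against.** The strongest reply is that this is permissive wording, not a rule that causes loss. The AE item names only study drug, AE stopping is absent from the mandatory study-exit list in 11.3, and recurrence assessment covers randomized women generally. The reason list in SAP 5.1 is generic (it also contains screen failure), so it does not show that AE exits from the study are expected. Protocol 12.5 points sites to the medical monitor or sponsor when tolerability AEs cause missed doses. Protocol 11.3 and 18.4 ask for TOC procedures at withdrawal.

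Most of that stands. A reader might infer that the plan sends AE stoppers out of the study; it does not. What remains is that exit is permitted and nothing rules it out. The TOC procedures brought forward to the exit date cannot rescue her, because SAP 8.1 scores an exit before TOC as a failure whatever they show.

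Two further replies also stand. The failure rule is the sponsor's stated choice, and it is not disputed here. The stop rates above 0% have no source in the documents: the only recorded figure is zero, and dosing is six single days four weeks apart.

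A reader might also infer that her data are discarded altogether. They are not, as the first table shows.

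**Conclusion.** The point holds as a low-priority design improvement. The plan permits, without requiring, an observable Week 24 outcome to become an imputed failure, and no planned analysis supplies the missing status.

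The size is unknown. If stoppers revert to 43%, the effect is nearly neutral when stops are rare or equal between arms. If stops are more common on ibrexafungerp, the effect is bias toward no difference, for illustration 0.068 of power at 5%/1%. A reader might infer a risk of a false positive; on that pattern the chance of a false claim for the drug falls. The opposite would need more AE exits on placebo, which nothing in the documents suggests.

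The power figures should not be read as upper bounds or forecasts. They are larger if stoppers keep some benefit and smaller if only some stoppers are exited. They are also smaller if the 65% and 43%, which are rates of documented Clinical Success, already count early leavers as failures. They use Fisher's test, as the sample size does, whereas the primary test is CMH.

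**What to change.** Add to Protocol 11.3:

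*Stopping study drug, including for an AE, is not by itself a reason to leave the study; subjects who stop study drug continue all scheduled contacts and visits to Week 36 unless they withdraw consent, are lost to follow-up, meet a mandatory study-exit reason, or the investigator or sponsor documents why continued visits (not continued dosing) are against their best interest.*

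The last clause matters: an open best-interest exemption would let a site exit an AE stopper much as it can now.

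SAP 8.1 scoring stays as it is. One consequence to expect is that a woman who stops for a study-drug-related AE and is followed can be an ITT success while the PP rule classes her a failure.

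The cost is one protocol sentence. It needs no new visit, procedure or eCRF item, since 11.3 already requires the reason for stopping treatment to be recorded. Sites would follow a few off-drug women: 120 × (0.05 + 0.01) = 7.2, about 7 of 240, at the assumed 5%/1%, and 120 × (0.08 + 0.02) = 12 at 8%/2%.

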11.4 Replacement of Discontinued Subjects

Subjects who discontinue early from randomized treatment will not be replaced.

12.0 Study Treatments

12.1 Study Treatment Groups

12.1.1 Acute Phase

Subjects who meet all study eligibility criteria at Screening will enter the Acute Phase of the study and will receive oral fluconazole, as follows:

- Oral fluconazole 150 mg QD on Days -14, -11 and -8

The first dose of fluconazole will be administered on Day -14 at the study site, after all other visit procedures have been done. Subjects will self-administer the remaining doses at home.

12.1.2 Prevention of Recurrence Phase

Subjects who have a culture-confirmed VVC from the sample collected at Screening, achieve a significant resolution of the signs and symptoms of infection (total composite score ≤ 2 on the VSS Scale) at Baseline (Day 1) and continue to meet all study eligibility criteria will be randomized at a 1:1 ratio to one of the following two treatment groups:

- Oral ibrexafungerp administered as a single-day treatment repeated every 4 weeks (28 days [± 3]) for a total of 6 single-day treatments (Baseline [Day 1], Week 4, Week 8, Week 12, Week 16 and Week 20). Each single-day treatment will consist of two doses of 300 mg each given 12 (± 4) hours apart (total single-day dose = 600 mg) (see [Table 1](#)).
- Matching oral placebo administered as a single-day treatment repeated every 4 weeks (28 days [± 3]) for a total of 6 single-day treatments (Baseline [Day 1], Week 4, Week 8, Week 12, Week 16 and Week 20). Each single-day treatment will consist of two doses of placebo given 12 (± 4) hours apart.

Table 1: Double-Blind Oral Ibrexafungerp Dosing Regimen

Dosing Day	Study Visit/Study Day	Single-Day Doses	Oral Tablets	Total Daily Dose
Dosing Day 1	Week 1/ Study Day 1 (Baseline)	300 mg AM 300 mg PM	2 x 150 mg 2 x 150 mg	600 mg
Dosing Day 2	Week 4/ Study Day 28 (± 3)	300 mg AM 300 mg PM	2 x 150 mg 2 x 150 mg	600 mg
Dosing Day 3	Week 8/ Study Day 56 (± 3)	300 mg AM 300 mg PM	2 x 150 mg 2 x 150 mg	600 mg
Dosing Day 4	Week 12/ Study Day 84 (± 3)	300 mg AM 300 mg PM	2 x 150 mg 2 x 150 mg	600 mg
Dosing Day 5	Week 16/ Study Day 112 (± 3)	300 mg AM 300 mg PM	2 x 150 mg 2 x 150 mg	600 mg
Dosing Day 6	Week 20/ Study Day 140 (± 3)	300 mg AM 300 mg PM	2 x 150 mg 2 x 150 mg	600 mg

Subjects will receive their first dose of double-blind study drug at the site and will self-administer the remaining doses at home. Subjects must take the two doses of study drug 12 hours apart (± 4 hours), preferably with or immediately after a meal. An electronic dosing reminder system (e.g. text message) may be implemented for consenting subjects to facilitate study drug dosing compliance.

